7.2.3 Tertiary Outcomes (Stage A2 and B)

These outcomes will not be analysed as part of this SAP.

7.3 Missing Data

Every effort will be made for complete collection and recording of data. Dose allocation and primary outcome evaluation using the TiTE-CRM model requires complete data; for this reason, a dedicated CRF has been designed, which captures only that data required to run the model.

No data imputation is planned.

7.4 Sensitivity Analysis

There will be four sensitivity analyses presented for each dose decision meeting. They will be analysed using the TiTE-CRM as in the primary analysis. These are:

1. Only using those patients who not missed any of their dose prescribed on their dose schedule, and weighted using the original TiTE-CRM weights, i.e. weighting only according to length of follow-up and not taking account of how much dose has been received
2. Only using those patients who have received at least 75% of the prescribed dose, using the same weight function as in the main analysis
3. Only using those patients who have received at least 75% of the prescribed dose, but using the original TiTE-CRM weights

A phase I dose escalation safety study combining the ATR inhibitor VX-970 with chemoradiotherapy in oesophageal cancer using time to event continual reassessment method (funded by CRUK and Merck)
EudraCT Number: 2015-003965-27

4. Using the same population and weighting as the primary population but assuming the “Most Toxic” Scenario. All patients currently on treatment within the DLT window have been assigned a DLT.

For each of these analyses we will present the posterior probabilities of toxicity at each dose level and their associated 95% credible interval.

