5.4.5 Stage A2 evaluations on early withdrawal

Where possible, patients will be followed up as per the follow up visits at 2 and 8 weeks post end of treatment, including assessments of AEs and DLTs (see section 6).

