9.1.2 Definition of a DLT

Stage A1

DLTs will be defined as per NCI CTCAE v4.03 and include:

- Absolute neutrophil count (ANC) $<0.5 \times 10^9/L$ for >7 days
- Febrile neutropenia (fever of unknown origin without clinically or microbiologically documented infection) (ANC $<1.0 \times 10^9/L$, fever $\geq 38.5^\circ C$) lasting >3 days
- Infection (documented clinically or microbiologically) with Grade 3 or 4 neutropenia (absolute neutrophil count $<1.0 \times 10^9/L$)
- Platelets $<25 \times 10^9/L$
- Clinically significant bleeding attributed to grade 3 thrombocytopenia or requiring platelet transfusion
- Grade ≥ 3 oesophagitis onset within 2 weeks of starting radiotherapy
- Grade ≥ 3 pneumonitis onset within 3 months of starting radiotherapy
- Grade ≥ 3 nausea or vomiting not controlled by optimal outpatient anti-emetic treatment
- Grade ≥ 3 diarrhoea despite optimal outpatient anti-diarrhoeal medication use
- Other grade 3 \geq effects thought to be directly treatment related to the combination of M6620 (Berzosertib) with radiotherapy
- Any toxicity causing a delay of radiotherapy completion by greater than one week
- Missing 2 consecutive doses of M6620 (Berzosertib) within a cycle due to Grade ≥ 3 toxicity
- A delay of any of the 3 treatments of 7 days or more within a cycle due to treatment related toxicity
- An elevation of ALT or AST $>5 \times ULN$ lasting 8 days or more
- A concurrent elevation of ALT or AST $>3 \times ULN$ and total bilirubin $>2 \times ULN$ in whom there is no evidence of biliary obstruction or other causes that can reasonably explain the concurrent elevation
- Death due to drug related complications
- Cardiac:
 - QTc prolongation (any QTc interval ≥ 500 msec or any change in QTc interval ≥ 60 msec from baseline) on ECG, unless related to an electrolyte abnormality and prolongation resolves with correction of electrolyte abnormality

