3.1.1 Stage A1

The aim is to find the M6620 treatment schedule when combined with radiotherapy that is associated with no more than 25% dose limiting toxicity rate on the basis that palliative oesophageal radiotherapy is associated with approximately 15-20% grade 3/4 toxicity. Six treatment schedules are proposed. Each schedule comprises a specific combination of dose and dosing frequency. There are two possible M6620 doses and three dosing frequencies (see section 4.1.1). The radiation dose remains consistent across all treatment schedules. For the prior estimates of DLT at each treatment schedule, see the skeleton in Table 1.

The treatment involves 3 weeks of daily radiotherapy and M6620 at a pre-determined frequency dependent on the treatment schedule allocated to the individual patient. The follow-up of a further 6 weeks provides a DLT observation window of a total of 9 weeks. An initial cohort of three patients will receive the starting schedule (lowest dosing frequency) at the starting dose, 140mg/m². The fourth patient will not be recruited until all three patients have been followed for the minimum of 9 weeks from the start of radiotherapy or the occurrence of a DLT.

Subsequently, all eligible patients will be continuously recruited and the TiTE-CRM will be used to assign their treatment schedule. To ensure enough information is accumulated to inform the assignment of the treatment schedule to the subsequent patient, recruitment will be managed through allocation of treatment slots (see Protocol section 4.4 for further details).

Stage A1 stopping rules

A phase I dose escalation safety study combining the ATR inhibitor VX-970 with chemoradiotherapy in oesophageal cancer using time to event continual reassessment method (funded by CRUK and Merck)
EudraCT Number: 2015-003965-27

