Stage A1 will pause for safety if, at any point in the trial, there is sufficient evidence to suggest that schedule 1 is too toxic. More specifically, we will consider schedule 1 to be too toxic if, given all the available data, there is a high probability that the DLT rate is greater than the target toxicity level of 0.25. If all 3 patients in the first cohort have DLTs then schedule 1 is too toxic and the trial will be re-started. At this point, three extra schedules will be introduced at 90mg/m² and varying dosing frequencies, namely (schedule -3, -2 and -1). Once the trial is restarted, the lowest schedule, schedule -3, will be explored first. There will then be 9 treatment schedules to explore (the original 6 plus the 3 dosing frequencies at the lower dose). If the first 3 patients recruited to schedule -3 experience DLTs then the trial will stop. If schedule 1 is found to be too toxic later in the trial when more than 3 patients have been recruited, a SRC meeting will be convened to decide whether the trial should be restarted using the lower dose of 90mg/m².

Stage A1 will stop for success when either a total of 10 patients have been assigned to a particular treatment schedule or 20 patients have been recruited, whichever occurs first. When 10 patients in Stage A1 have been assigned to a particular treatment schedule, recruitment will be paused until there are no more than three patients without full follow-up (either DLT or 6 weeks after the end of treatment), i.e. until there is full follow-up information on at least seven patients. If the MTD changes, recruitment may start again.

Based on simulations and assuming a patient will be recruited every 8 weeks, the average number of patients required for Stage A1 is 18, which we aim to recruit in 24 months.

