4.1 Stage A1 Treatment

Two M6620 dose levels and 3 dosing frequencies (treatment schedules) are proposed. Both the dose and frequency of M6620 will vary but the administered radiation dose and fractionation schedule will remain unchanged across treatment plans. The treatment schedule will last for 3 weeks and radiotherapy must start on a Monday.

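### SAP 7.4: the Most Toxic analysis leaves out Stage A1 patients who have finished treatment but are still inside the DLT window, so it can coincide with the primary analysis

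*SAP*

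**What the plan says.** SAP 7.4 lists four analyses to be shown at each dose decision meeting.

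- Analysis 4 keeps the primary population and weighting and adds the Most Toxic rule: "All patients currently on treatment within the DLT window have been assigned a DLT".
- Analysis 1 is restricted by dose: "Only using those patients who not missed any of their dose prescribed on their dose schedule". It weights by follow-up time alone.
- Analysis 2 is also restricted: "Only using those patients who have received at least 75% of the prescribed dose, using the same weight function as in the main analysis". Analysis 3 has the same restriction with follow-up-only weights. None of the three makes an exception for a patient who had a DLT.

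On timing in Stage A1, SAP 4.1 says: "The treatment schedule will last for 3 weeks and radiotherapy must start on a Monday". SAP 3.1.1 (Stage A1) says: "The follow-up of a further 6 weeks provides a DLT observation window of a total of 9 weeks". Its sample size paragraph works by "assuming a patient will be recruited every 8 weeks". In Stage A2 the DLT window is the first 4 weeks of an 18-week treatment. Patients who stop early are still followed, in A2 "at 2 and 8 weeks post end of treatment, including assessments of AEs and DLTs" (Protocol 5.4.5) and in A1 under Protocol 5.4.2. Protocol 6.1 treats the end of treatment as entry into follow-up.

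Protocol 9.1.2 counts "Missing 2 consecutive doses of M6620 (Berzosertib) within a cycle" because of grade 3 or worse toxicity as a DLT. Protocol 9.3 then ends M6620 for that patient.

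Under SAP 3.2 the TMG may confirm the model's schedule or over-rule it.

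**The concern.** A worst-case run should show what the model would say if every unresolved patient turned out to have a DLT. In A1 a patient is unresolved for 9 weeks but on treatment for only 3, so for 6 of the 9 weeks (67%) the rule does not reach them. Late-onset toxicity is the reason the SAP gives for using TiTE-CRM, and it is the off-treatment part of the window that the rule omits. The TMG could then see a result labelled Most Toxic that is no more cautious than the primary.

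Analyses 1 to 3 raise a related, smaller issue. Dose received can be cut short by toxicity, so selecting on it can remove DLTs. Three analyses that share this selection may agree with each other and look like confirmation.

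**Working it through.** **Inputs.** From SAP 3.1.1 and Table 1: A1 skeleton s = 0.12, 0.15, 0.18, 0.20, 0.22, 0.25; power curve p_k = s_k^exp(α); prior α ~ N(0, 1.158²); target 0.25; window T = 9 weeks. Weight: 1 for a DLT, otherwise w = ½(u/T + v/D), with u the weeks followed and v/D the share of M6620 given. Likelihood: a factor p for each DLT and 1 − w·p for each DLT-free patient. Posterior means come from numerical integration. Patient histories below are illustrative.

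**Check against the plan's own figure.** SAP 3.6 gives 18 (10, 20) patients for A1 and 16 (11, 20) for A2. With true rates assumed equal to the skeleton (the simulation scenarios are in a separate appendix), 1,000 simulated trials gave an A1 mean of 17.3, median 18, range 10–20, and an A2 mean of 16.2, range 11–20. The model as coded therefore behaves as described.

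**Who is on treatment at an A1 decision?** This depends on the gap between patients and on how long before the next start the decision is made (assumed 0 to 2 weeks).

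| Gap | Lead | On treatment | Off treatment, in window |
|---|---|---|---|
| 8 weeks | 0, 1 or 2 weeks | 0 | 1 |
| 4 weeks | 0 or 1 week | 0 | 2 |
| 4 weeks | 2 weeks | 1 | 1 |
| 2 weeks | 0, 1 or 2 weeks | 1 | 3 |

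Where the on-treatment count is 0, analysis 4 equals the primary.

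**Example 1, nobody on treatment.** Three complete DLT-free patients on schedule 1 (w = 1); one DLT-free on schedule 2 at week 8 after full dosing, w = ½(8/9 + 1) = 0.944.

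| | Schedule 1 (95% credible interval) | Schedule 2 |
|---|---|---|
| Primary, and analysis 4 as written | 0.062 (0.00–0.36) | 0.075 |
| Pending patient imputed | 0.247 (0.02–0.63) | 0.280 |

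As written, all six schedules are below 0.25, and the SAP 3.2 rule applied to that run would point to untried schedule 3. With the patient imputed it would point to schedule 1. At week 6 instead of week 8, the as-written schedule 1 value is 0.064.

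**Example 2, one on and one off treatment.** The same three patients; one on schedule 2 at week 6, w = ½(6/9 + 1) = 0.833; one on schedule 3 at week 2 with 4 of 6 doses, w = ½(2/9 + 4/6) = 0.444. Schedule 1 is 0.058 in the primary, 0.205 in analysis 4 as written, and 0.342 with both imputed. As written, the analysis adds caution but is not a worst case.

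**Analyses 1 to 3.** A1 schedules have n = 3, 5 or 6 doses. After two consecutive missed doses that end M6620, the largest share received is (n − 2)/n = 1/3, 3/5 or 4/6. All are below 75%. Counting only the k doses due to date gives at most (k − 2)/k, which is no larger. That DLT therefore always leaves all three analyses in A1.

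- *Estimate lowered.* First cohort, one such DLT in three on schedule 1: 0.314 with the DLT kept, 0.102 after the filter in all three analyses (complete full-dose patients have w = 1 under either weighting).
- *Estimate raised.* Schedule 1 with one DLT kept, three DLT-free at full dose and two DLT-free at 1/3 dose, w = ½(1 + 1/3) = 0.667: 0.219 becomes 0.262 when the two are dropped.
- *Exempting DLTs from the filter.* Schedule 1 with one missed-dose DLT, two DLT-free at 1/3 dose and four DLT-free at full dose. The primary gives 0.190 and 0.221 at schedules 1 and 2, pointing to schedule 2. Keeping the DLT while dropping the two under-dosed patients gives 0.223 and 0.256, pointing to schedule 1.

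**The case against.** **No decision rule uses these runs.** Correct, and it stands. Allocation, the MTD definition and the 0.95 stop rest on the primary model, which keeps every patient with at least one dose (SAP 5.2). The intervals shown are wide, so the TMG would see the uncertainty. A reader might infer that the allocation model understates toxicity; the documents do not support that.

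**'On treatment' may have been meant loosely, as everyone still in the window.** Possibly, and the Protocol Decision Point Plan, not available here, may say more. Nothing in the SAP or Protocol does, Protocol 6.1 separates treatment from follow-up, and a programmer would code the sentence literally. It needs changing on either reading.

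**The 8-week gap is a simulation assumption.** This stands. The same sentence aims for 18 patients in 24 months, about 104/18 = 5.8 weeks each, while 18 × 8 = 144 weeks is about 33 months. Protocol 4.4 sets a 4-week minimum that the TMG may shorten. A reader might infer that analysis 4 always equals the primary; it does not when someone is on treatment.

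**Example 1 imputes a DLT to a patient clear for 8 of 9 weeks.** Fair. If DLT times were uniform over the window, the chance of a DLT in the last week is about 2% at a true rate of 0.15, from (0.15/9)/(1 − 0.15 × 8/9), and about 4% at 0.25. Some A1 DLTs can also arise only early. Pneumonitis and other grade 3 or worse effects can still occur later. This argues for calling the run an upper bound.

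**Analyses 1 to 3 ask a legitimate question about adequately dosed patients.** They do. A reader might infer that the filter always biases downward and that every DLT should be exempted. The direction is not fixed, and exempting DLTs thins only the DLT-free group, which builds in an upward bias.

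**Conclusion.** The point holds for analysis 4 as worded, chiefly in Stage A1. When no in-window patient is on treatment, the Most Toxic result is the primary result. That is likely at 8-week spacing and less so at shorter gaps or longer decision leads. In the week-8 example the difference is 0.062 against 0.247 at schedule 1; with one patient on and one off treatment it is 0.205 against 0.342. In A2 the window lies inside treatment, so only early stoppers are missed.

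For analyses 1 to 3 the conclusion is narrower. In A1 they always lose the missed-dose DLT, so their agreement with each other or with the primary is not evidence of robustness. Other early DLTs may also drop out, depending on schedule and doses given (4 of 5 doses still passes 75%); DLTs after full dosing stay in.

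This rests on the literal wording, the SAP's model and prior, and assumed patient histories. The gap is in what the TMG is shown at a dose decision.

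**What to change.** **Analysis 4.** Replace the sentence in SAP 7.4 with a rule that assigns a DLT to every DLT-free patient whose DLT window is incomplete, whether on or off treatment. Label the result an upper bound. The drawback is a very conservative figure when patients are near the end of the window, and the label should say so.

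**Analyses 1 to 3.** Keep the dose filter. Beside each result, show how many DLT and DLT-free patients were excluded at each schedule. State that the results are conditional on dose received and are not evidence that the primary is robust. Also state whether the 75% is of the whole schedule or of doses due to date. Do not exempt DLTs from the filter.

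**Cost.** A changed rule, a label, a caveat and a small count table in SAP 7.4, with a matching code change. No new data are needed, and the primary model and stopping rule stay as they are.

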7.5 Pre-specified Subgroup Analysis

No formal subgroup analysis is planned.

7.6 Supplementary/ Additional Analyses and Outcomes

No formal supplementary/additional analyses are planned.

7.7 Health Economics and Cost Effectiveness (where applicable)

No health economics and cost effectiveness analysis is planned.

7.8 Meta-analyses (if applicable)

No meta-analyses are planned.

8. VALIDATION OF THE PRIMARY ANALYSIS

The schedule recommendation for each recruited patient will be calculated using a bespoke, validated program developed in **R** and **OpenBUGS** by [name]. The program has been validated using another **R** program developed independently by [name]. Further, the output from these two programs has been validated using the **titecrm** function in the **R** package **dfcrm**. Details on this package are available here: <https://cran.r-project.org/web/packages/dfcrm/>.

To validate the primary outcome and key secondary outcomes a statistician not involved in the trial will independently repeat the analyses detailed in this SAP. The results will be compared and any discrepancies will be reported in the Statistical report (See OCTRU SOP STATS-005 Statistical Report).

9. SPECIFICATION OF STATISTICAL PACKAGES

All analysis will be carried out using **R**. The relevant package and version number will be recorded in the Statistical report.

APPENDIX: GLOSSARY OF ABBREVIATIONS

SAP	Statistical Analysis Plan
DSMC	Data and Safety Monitoring Committee
TSC	Trial Steering Committee
CI	Chief Investigator
